The primary goal of the proposed project is to test personalized medication experiments to inform decisions about future medication use. Our central hypothesis is that our intervention will lead to within subject increases in adolescent involvement in decision making and decreases in uncertainty about future medication use. We view this open label trial as a pilot study to test the feasibility, acceptability, and preliminary efficacy of the medication experiment intervention and therefore warrants further testing in a future larger trial.

BACKGROUND:

Statement of the problem

ADHD is the most common mental health condition of childhood¹² affecting 6.4 million children aged 4-17 years in the United States.² Children with ADHD experience impairments across a wide range of areas of functioning including academics, social relationships, and family functioning.¹³ Fortunately, efficacious treatments for ADHD exist. Medications, either alone or in combination with behavior therapy, reduce ADHD symptoms and some areas of impairment¹,

¹⁴ and are recommended as a first-line treatment in clinical practice guidelines.^{6, 7, 15} Medication use is quite common among children with ADHD, but use plummets after age 11 even though adolescents continue to demonstrate symptoms and impairment.^{2, 16} Moreover, those who continue to take medicine take their medications inconsistently (i.e., only 50% of days covered with medicine¹⁷).

Developmental influences

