[name] developed a web-based intervention (mehealth for ADHD) which enables community-based pediatricians to deliver higher quality ADHD care⁴⁴ leading to children with significantly fewer ADHD symptoms. 45 Subsequently, partnerships with the American Academy of Pediatrics and American Board of Pediatrics helped spread use of the portal beyond practices that participated in research and now includes 60,801 patients cared for by 2,153 pediatricians in 886 practices across the US. These practices use the portal as a registry to manage their entire ADHD patient population. With pediatricians continuing to enroll patients on the portal as part of routine clinical care, opportunity exists to leverage this infrastucture to efficiently develop and test new interventions. The proposed research would fill a sizable gap as the current portal is focused exclusively on young school age children with ADHD and medication adherence has not been targeted nor improved. Specifically, while a randomized controlled trial testing the efficacy of the mehealth for ADHD web intervention demonstrated significant effects on children's treatment outcomes, there was not a significant intervention effect on medication adherence (i.e., 59% of days covered by children in the mehealth for ADHD portal group vs. 54% in the control group). 45 Moreover, the portal is devoid of features for adolescents. In focus groups, pediatricians, parents, and adolescents have repeatedly requested such features.

STUDY DESIGN:

We will conduct a pilot, single-arm, open-label trial of the medication experiment feature among 30 adolescents experiencing uncertainty about continued medicine use (see **Figure 2**). Because the medication experiment feature is not clinically relevant for adolescents taking a non-stimulant ADHD medication, they will be excluded. At the time of enrollment, families will complete baseline measures electronically and schedule an in-person visit. We will verify the medication prescribed and the number of days covered with medicine in the past year using

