At baseline we will collect items from standard UTBC scales⁴⁶ to assess the relevance of pre-intention factors and the strength of their intention to take/give medicine, and items from the validated Adolescent and Parent Medication Barriers Scales^{47, 48} to assess the relevance of

implementation factors (see **Measurement**). Once baseline surveys have been completed, we will create a meHealth account for the dyad and schedule an in-person study visit at the Center for ADHD. Study visits will not be scheduled if there is missing survey data as parent and adolescent engagement providing responses electronically is critical to success of completing the medication experiment which involves tracking outcomes. The study physician will meet with the dyad to gather history and better understand their past experience with medication. The study physician and research assistant will collect the DMIS introductory interview to identify the most recent ADHD medication decision made by family (e.g. stop for summer, resume for school year, adjust dosage, change medication, etc.) and then each will complete the decision making involvement scale independently.

During our development process, we identified the following types of experiments that are often relevant:

- 1. Make no changes. Track current state: continue to take medication as it is currently prescribed.
- 2. Take medication on non-school days. Track effects: If not currently taking medication on non-school days, start taking medication on those days and track the effects.
- 3. Stop taking medication on non-school days. Track effects. If currently taking medication on non-school days, stop taking medication on those days and track the effects.
- 4. Do a formal trial off of medication. Take current medication as currently prescribed for 2 weeks while tracking, then stop taking medication for 2-4 weeks while continuing to track.
- 5. Change dose or change medication. Consider a different medication or different dose of current medication in consultation with study doctor. Track the effects.

The study physician will discuss these options with the dyad, they will then select the medication experiment they would like to complete. Next, the study physician and research assistant will use the meHealth software with the dyad to identify, prioritize, and discuss behavioral targets to monitor during the experiment.

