At the conclusion of the medication experiment, the research assistant will schedule an inperson study visit at the Center for ADHD. The study physician, adolescent and parents will discuss what was learned using a report generated by mehealth for ADHD to visualize the outcome data that was collected. Subsequently, the adolescent and parent will be asked to independently indicate their preference for what to do next (continue [medication regimen from experiment], resume previous medication/dosage, conduct another experiment, return to pediatrician to adjust dosage or change medication, other), and their preferred role in decision-making. The study physician will then facilitate a discussion to resolve any differences between adolescent and parent preferences and come to a consensus. The parent will receive a study summary document to share with their child's pediatrician so s/he is aware of what was learned and can use this to guide future management decisions. The adolescent and parent will report this decision, their certainty about the decision, their preferred role in decision-making, their involvement in the process of making this decision, and their intentions about taking/giving medicine. We will also ask the parent and adolescent about the usability the medication experiment software (see Measures).

Measurement Strategy: Aggregation of individual trials to estimate a population level treatment effect isn't needed given the strong evidence of stimulant effectiveness among adolescents.¹ Rather, it is important to ascertain whether the use of medication experiments helps adolescents and parents work together to resolve uncertainty about future use of medicine. We will describe the type and number of medication experiments conducted as well as the personal outcomes selected for tracking. We will examine process outcomes like the decision-making involvement, comfort with the decision made, and whether the decision was implemented.

Measures to characterize the sample on demographic, ADHD, and psychosocial factors

- 1. Demographics: Adolescents, parents, and pediatricians will report on age and race/ethnicity. Parents will also report on child insurance status, and their own level of education and mental health history.

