Decision-Making Preferences—The Control Preferences Scale⁶⁹ assesses the degree of control an individual wants to assume when decisions are being made about medical treatment. The Control Preferences Scale will be modified so that adolescents and parents choose preferred control options that range from the adolescent solely making the decisions regarding choice of medication experiment, to the adolescent making the decisions jointly with the parent, to the parent solely making the decisions.

Outcome Measures

- 12. Decision-Making Involvement Scale (DMIS) (Miller et al., 2012): is a 30-item scale to measure adolescent involvement in a decision. The five subscales are: "Child Seek" (child asks for an opinion or information from parent), "Child Express" (child expresses an opinion or information to parent), "Parent Seek" (parent expresses advice or opinion to child), "Parent Express" (parent expresses advice or opinion to child), and "Joint/Options" (negotiation or brainstorming between parent and child). We will use the Decision-Making Involvement interview guide to collect this measure at study visit 1 and the stand-alone version to collect it study visit 2.

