- 13. Certainty about the decision will be measured using the Decisional Conflict Scale (DCS): The DCS⁷⁰ has an initial question to ascertain the option that has been selected. Options presented will be: continue [medication regimen from experiment], resume previous medication/dosage, conduct another experiment, return to pediatrician to adjust dosage or change medication, other [write in]. The DCS then has 16 questions that are divided into five subscales: informed subscale, values clarity subscale, support subscale, uncertainty subscale, and an effective decision subscale. The informed subscale measures how informed participants feel about the benefits and risks of the decision. The values clarity subscale measures a participant's feelings about personal values for benefits and risks/side effects. The support subscale measures perceived levels of support during decision-making. The uncertainty subscale measures a participant's level of certainty about the best choice to make. The effective decision subscale measures the satisfaction with the decision made. The total DCS score equally weighs all five subscales. Responses to each question are reported on a 5-point Likert scale (0 = strongly agree to 4 = strongly disagree). The total DCS scores are calculated by summing item scores and then converting the scores to a 0-100 scale, where 0 implies no decisional conflict and 100 implies extremely high decisional conflict. Scores <25, 25 to 37.5, >37.5 indicate low, moderate and high decisional conflict, respectively. Scores 25 and higher reflect clinically significant decision conflict.
- 14. Behavioral Intention questions that will assess the adolescent and parent intention to take/give ADHD medicine regularly will be measured using the standard measure of intention from the UTBC. 46 Responses are on a 7-point scale from strongly agree (+3) to strongly disagree (-3) that assess intention to take medicine for ADHD on weekdays, weekends, and school vacations.
- 15. System Usability Scale (SUS)⁷¹ is a validated 10-item unidimensional scale with response options on a 5-point agreement scale which results in a score from 0 to 100, with higher scores indicating greater usability.

Implementation of decision: 3 months after study visit 2, we will obtain pharmacy dispensing records to ascertain whether their joint decision was implemented. If medication was continued, we will calculate the percentage of days covered.

DATA ANALYSIS

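### The DMIS is collected with the interview guide at visit 1 and the stand-alone version at visit 2, so the single-arm paired test of Hypothesis 1 cannot separate any version effect (possibly zero) from the pre-post change

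*Combined protocol and SAP*

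**What the plan says.** Item 12 under Outcome Measures describes one 30-item DMIS with five subscales. It plans to use the "interview guide to collect this measure at study visit 1 and the stand-alone version to collect it study visit 2".

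The Intervention section gives the visit 1 procedure. The study physician and research assistant "will collect the DMIS introductory interview to identify the most recent ADHD medication decision made by family", "and then each will complete the decision making involvement scale independently". I read 'each' as adolescent and parent, because Power and Sample Size has DMIS change calculated for both.

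The later part of the same section describes visit 2. The physician will "facilitate a discussion to resolve any differences between adolescent and parent preferences", after which both respondents "will report this decision, their certainty about the decision, their preferred role in decision-making, their involvement in the process of making this decision". The Decisional Conflict Scale (item 13), also an end-of-study outcome, has an "initial question to ascertain the option that has been selected". No introductory DMIS interview is described for visit 2.

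Study Design calls this a "pilot, single-arm, open-label trial of the medication experiment feature". Hypothesis 1 predicts a rise from pre to post in the child express and parent seek subscales, tested by a paired t-test. Cohen's d is to be reported for each pre-post outcome.

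**The concern.** A pre-post comparison needs the outcome to be taken in the same way both times. Here every pre score comes from one version of the DMIS and every post score from the other, and there is no control arm in which the same switch would occur without the intervention. If the version moves scores upward, the movement looks like benefit; if downward, it hides benefit.

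The outcome is central. Purpose of Study names "within subject increases in adolescent involvement in decision making" as one of the two parts of the central hypothesis, and Hypothesis 1 is its test. The effect size is to come from a pilot intended to inform a larger trial, so an artefact in d could be carried forward. The documents give no reason for the switch, do not state that the two versions are equivalent, and plan no sensitivity analysis for it.

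**Working it through.** **Step 1. Compare the two visits as described.**

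| | Visit 1 | Visit 2 |
|---|---|---|
| Version (item 12) | interview guide | stand-alone |
| How the decision is identified | staff-led introductory interview | reached by consensus and reported by participants; the DCS also asks for the option selected |
| Completion of items | independently by each respondent | reported by adolescent and parent; no interviewer described |
| Decision rated | latest past medication decision | decision just made with the physician's help |

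Two things differ: the version or lead-in, and the decision rated. The second is partly intended by the design. The first need not differ.

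**Step 2. Is a version effect identifiable?** Let δ be the pre-post change and b the version effect, with mean score μ at visit 1.

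- Expected visit 1 score: μ
- Expected visit 2 score: μ + δ + b
- Expected paired difference: δ + b

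With columns for intercept, time and version, each dyad contributes the rows (1, 0, 0) and (1, 1, 1). The time and version columns are identical, so the three-column model has rank 2. The data estimate δ + b and nothing finer. This holds whatever the size of b, including b = 0.

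**Step 3. Which hypotheses are touched?** Hypothesis 1 and its d use the pre-post DMIS difference. Hypotheses 3 and 4 compare post scores between groups, all collected with the stand-alone version, so the switch between visits does not enter.

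**Step 4. Illustration of scale.** There is no plan figure to reproduce: the target of 30 is chosen to exceed a recommended pilot size of 20, and no alpha, sidedness or SD is stated. Assumptions: two-sided 5%, with b and d in SDs of the change score. The formula is the upper tail of the noncentral t with n − 1 degrees of freedom and noncentrality (d + b)√n. For b = 0.2, d = 0, n = 30 the noncentrality is 0.2 × 5.477 = 1.095. The size n = 24 is 80% of 30, the plan's retention criterion.

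Chance of a significant increase, no true effect (d = 0):

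| b | n = 30 | n = 24 |
|---|---|---|
| 0 | 2.5% | 2.5% |
| +0.1 | 7.6% | 6.8% |
| +0.2 | 18.4% | 15.4% |
| +0.3 | 35.5% | 29.1% |

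Chance of a significant increase, true d = 0.5:

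| b | n = 30 | n = 24 |
|---|---|---|
| 0 | 75.4% | 65.0% |
| −0.1 | 56.3% | 46.7% |
| −0.2 | 35.5% | 29.1% |
| −0.3 | 18.4% | 15.4% |

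The d of 0.5 is only the plan's label for a medium effect. I read the 80% power statement as describing the larger trial, not a target for this pilot.

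A shift b moves Cohen's d by b if d is standardised by the change-score SD. If the baseline SD is used (equal variances, pre-post correlation r), the movement is b√(2(1 − r)). For b = 0.2 that is 0.25, 0.20 or 0.13 at r = 0.2, 0.5 or 0.8. The plan calls 0.20 small.

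These figures would hold for any shift tied to time point. Nothing in the documents anchors b at any of these values.

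**The case against.** The strongest reply is that little difference remains once the Intervention section is read. From item 12 alone a reader might infer that items were asked by an interviewer at visit 1 and self-completed at visit 2. The documents do not support that: the visit 1 interview is introductory, and the scale is then completed independently. A reader might also infer that the two versions have different items or scoring. That is not shown; item 12 describes a single measure collected twice. What remains is how the decision is named beforehand, and there is an evident reason for that: a past decision has to be elicited, whereas the visit 2 decision has just been made and reported. All of this stands, and it makes a small effect likely.

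A second reply is that any single-arm pre-post comparison is already open to time, regression to the mean and expectancy, and that the contrast between a recalled decision and a just-made, physician-facilitated one is larger than any effect of lead-in. This also stands, and matching the format would not remove it. But those features come with the chosen design, whereas the change of version is an addition that can be avoided without a control group.

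Third, the rejection rates are generic. Agreed: they should not be read as the bias expected here.

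**Conclusion.** The point holds in a limited form. The complete overlap of DMIS version with time point follows from the text and needs no assumption: the paired test and d for Hypothesis 1 cannot distinguish a version effect from the pre-post change. The size and direction of that effect cannot be obtained from the documents; it is probably small and may be zero. It would be wrong to conclude that Hypothesis 1 is shown to be biased, or that matching the format would make its result attributable to the intervention.

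This is a worthwhile, inexpensive improvement to a central outcome, not a flaw that undermines the pilot. Two nearby matters are editorial and carry no weight here: the SD that standardises Cohen's d is not named, and item 12 gives Parent Seek the same definition as Parent Express.

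**What to change.** Amend the Intervention section and item 12 so that both visits use the same DMIS items and scoring, the same short scripted lead-in naming the decision to be rated, and independent self-completion by adolescent and parent. The lead-in can name a past decision at visit 1 and the consensus decision at visit 2; its form should be identical.

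In the interpretation of Hypothesis 1, state that a recalled past decision is being compared with one just made with a physician's help, and that matching the format does not remove this contrast. If data collection is already complete, this limitation and the change of version can still be reported.

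The cost is protocol wording and a few minutes of staff time at visit 2. Sample size, number of visits and analysis method are unchanged.

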- 9. Implementation factors of UTBC influencing medication continuity (See Compendium of Measures):): These factors will be measured using the Adolescent and Parent Medication Barriers Scales (AMBS and PMBS). 47, 48 Adolescents and parents respond using a 5-point Likert-type scale with ratings from "strongly disagree" to "strongly agree" to report perceived barriers to medication taking. Both the adolescent scale (17-items) and parent scale (16-items) have strong internal consistency for total score and the four factor-analytically derived subscales: 'Disease frustration/adolescent issues', 'Regimen adaptation/cognitive', 'Ingestion issues', and 'Parent reminder'. For criterion-related validity, adolescents classified as non-adherent had significantly higher barrier scores than those classified as adherent. In prospective validation studies, the adolescent-perceived barriers of 'Disease frustration/adolescent issues' and parent-perceived barriers of 'Regimen adaptation/cognitive issues' were associated with poorer adherence to medication taking. 48
- 10. Past Year Medication Continuity: We will calculate the percentage of days covered with medicine based pharmacy dispensing records. We have successfully obtained pharmacy dispensing records via parental permission for 95% (155/164) of subjects across 2 studies (R01 MH074770, K23 MH083027).^{63, 64} Pharmacy dispensing records provide an objective, unobtrusive, reliable measure that is a well-accepted proxy for medication consumption⁶⁵ that was significantly correlated with the more expensive and invasive Medication Event Monitoring System (MEMSCapTM) which uses a microprocessor in the medication container cap to record the day and time of each vial opening.⁶⁶
- 11. Medication Diversion: Adolescent self-report of giving away, trading, or selling ADHD medicine to someone for whom it was not prescribed will be collected via a confidential web-based survey used in past population-based studies of middle/high school students. 67, 68

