We will conduct descriptive analyses to summarize measures that characterize the sample in terms of demographic, ADHD, and psychosocial factors, the experiments selected, and decisions made, as well as feasibility and usability data. In order to determine overall feasibility and usability of our pilot intervention, we will compare retention, participation, and usability ratings to a priori criteria based on previous research (i.e., retention $\geq 80\%$, participation $\geq 80\%$, usability ≥ 70), 72 using Chi-square tests.

Power and Sample Size

We selected a target sample size of 30 to exceed the recommended sample size (n = 20) for a pilot trial designed to inform a larger efficacy trial with 80% power to detect a medium effect. Of note, we aren't powering the study to examine differences in outcomes by experiment type. Paired-samples t-tests will be used to calculate the change in DMIS,DCS, and behavioral intentions for all adolescents and parents, and for medication continuity among the subset who choose to continue medication after completing their experiment. Cohen's d will be calculated to estimate effect size for each pre- to post-outcome and interpreted as small (.20), medium (.50), and large (.80).

Hypothesis testing

We will test the following hypotheses:

- 1. From pre to post, within-subject report on DMIS subscales "child express" will increase and "parent seek" will increase.
 - a. Paired sample t-test
- 2. From pre to post, within-subject DCS will decrease.
 - a. Paired sample t-test
- 3. Higher post-DMIS joint/decision scores will be reported by dyads who differ on initial preferences following the experiment compared to those who don't.
 - a. Two sample t-test
- 4. Higher post-child express scores will be reported by adolescents who want to make the decision alone compared to those who prefer to share decision or have parent make decision.
 - a. Two-sample t-test
- 5. Adolescent-parent conflict as measured at baseline by the CBQ will be positively associated with discordance in independent preferences following the medication experiment.
 - a. Biserial correlation coefficient
- 6. The difference between the adolescent's intention to take ADHD medication and the parent's intention to give ADHD will decrease from pre to post.
 - a. Linear mixed model

Scientific Rigor:

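### Dispensing records alone cannot show whether a decision that differs only on non-school days was implemented

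*Combined protocol and SAP*

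**What the plan says.** Under Outcome Measures, Implementation of decision, the only data source is the pharmacy: "3 months after study visit 2, we will obtain pharmacy dispensing records to ascertain whether their joint decision was implemented". A second step follows: "If medication was continued, we will calculate the percentage of days covered". No self-report, pill count or supply check at 3 months is described. No rule is given for matching a fill history to the option chosen.

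The options to be checked at the end of the experiment are "continue [medication regimen from experiment], resume previous medication/dosage, conduct another experiment, return to pediatrician to adjust dosage or change medication, other". What the first two mean depends on the experiment. In the Intervention section, experiment 2 adds medication on non-school days and experiment 3 removes it: "If currently taking medication on non-school days, stop taking medication on those days and track the effects". Experiment 4 is a trial off medication after a tracked period on it: "then stop taking medication for 2-4 weeks while continuing to track".

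The Measurement Strategy lists "whether the decision was implemented" among the process outcomes. Baseline continuity (item 10, Past Year Medication Continuity) uses the same kind of data: "We will calculate the percentage of days covered with medicine based pharmacy dispensing records". Under Power and Sample Size, a paired t-test and Cohen's d are planned "for medication continuity among the subset who choose to continue medication after completing their experiment".

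**The concern.** After experiment 2 or 3, continuing the experimental regimen and resuming the previous one differ only in what happens on non-school days. To say which was implemented, the data must carry information about particular days, and a dispensing record does not. The protocol recognises the difference elsewhere. Its intention items ask separately about weekdays, weekends and school vacations, and its account of past-year continuity contrasts pharmacy records with a cap device that logs the day and time of each opening.

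Two things are at stake. A named process outcome cannot be determined for dyads who make such a decision. In addition, the pre-post change in continuity will contain shifts that come from the regimen chosen. A reader could mistake these for decisions well or badly carried out, and could carry that reading into the design of the larger trial.

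**Working it through.** The plan gives no implementation rate, coverage formula or threshold for this outcome, so there is no stated figure to reproduce.

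**Inputs.** From the plan: dispensing records obtained 3 months after visit 2, part-week regimens (experiments 2 and 3), and a 2 to 4 week period off medication (experiment 4). Assumed: a 90-day window, supply labelled for daily use, school days as 5 of every 7, fills of 30 units, and 0 to 28 days of leftover supply.

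**1. Two different behaviours give the same record.**
- School-days-only use, perfectly followed: 90 × 5/7 = 64.3 days; 64.3/90 = 71.4%.
- Daily decision with 2 of 7 doses missed: 5/7 = 71.4%.
- In both cases a 30-unit fill lasts 30 × 7/5 = 42 days, so the refill pattern is the same.

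**2. Coverage separates the two regimens only if adherence is known to be full.** The Background cites coverage of 50% in adolescents who continue, and 59% and 54% in the two groups of the earlier portal trial. Each value fits either regimen:
- 50%: half of daily doses, or 0.50/0.714 = 70% of school-day doses.
- 54%: 54% of daily doses, or 0.54/0.714 = 76% of school-day doses.
- 59%: 59% of daily doses, or 0.59/0.714 = 83% of school-day doses.

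**3. Sensitivity to the assumptions.**
- With vacation weeks in a 13-week (91-day) window, perfect school-days-only use gives 10 × 5/91 = 54.9% for 10 school weeks and 6 × 5/91 = 33.0% for 6.
- If the pharmacy recorded a school-days schedule, 30 units would count as 42 days and coverage would read 100%. The record would still not show which days were medicated.

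**4. Effect on the paired test of continuity.** A fully implemented move from daily to school-days-only use changes coverage by 71.4 − 100 = −28.6 points; the reverse move gives +28.6. If a net 10% to 40% of continuers (an assumed range) moved to school-days-only use, the mean change would shift by 0.10 × 28.6 = 2.9 to 0.40 × 28.6 = 11.4 points downward. For scale, the two portal-trial groups differ by 59 − 54 = 5 points.

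**5. Leftover supply, only if it is not carried forward.**
- Experiment 4, then perfect resumed daily use: 14/90 = 15.6 points lost with 14 days left over, and 28/90 = 31.1 points with 28. Coverage would read 84.4% or 68.9%.
- Experiment 3 over the two-week minimum after a change: about 4 unused weekend doses, 4/90 = 4.4 points.
- No leftover, or leftover credited: no loss.

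**The case against.** Several stronger readings are tempting, and the documents do not support them.

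- **Days covered is the implementation criterion.** A reader might infer this, but the text has two steps: implementation is ascertained from dispensing records, and coverage is then calculated if medication continued. For decisions to stop, or to change drug or dose, fills are informative without any coverage threshold. The problem is confined to decisions about non-school days and, conditionally, to resumption with leftover stock.
- **The plan ignores unused supply.** It is silent. Past-year records are already collected, so earlier fills could be credited. Prescriptions are written as needed and filled at the family's own pharmacy, so a family off medication may simply not refill and have little left over.
- **A school-days-only family will be scored as poorly continuous.** No threshold is stated, and 71% exceeds every coverage figure the protocol cites (50%, 54% and 59%).
- **The continuity test is wrong.** Continuity means days covered. A family that drops non-school days does have fewer of them, and a lower value measures that correctly. Replacing the denominator in this test would change the construct and could hide real reductions in use. It would also need a past-year regimen history that no planned measure supplies.
- **Implementation is what the trial most needs to learn.** The Measurement Strategy puts resolving uncertainty first. Implementation is one of several process outcomes and is absent from the six listed hypotheses.

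These points narrow the concern but do not remove it. None of them gives fills information about particular days, and no other source for this outcome is planned.

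**Conclusion.** The concern holds in a limited form. For decisions that differ only on non-school days, the single planned source cannot determine implementation, because full school-days-only use and daily use with 2 of 7 doses missed both give about 71%. In the continuity comparison, a fully implemented switch moves an individual by about 29 points. That is a legitimate change in continuity, but it is not evidence about implementation.

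The sizes rest on a 90-day window, daily-labelled supply and continuous school weeks. The plan gives no figure for how many dyads will make such decisions, so the effect on the group mean is known only as a range. The leftover-supply effect runs from 0 to 31 points and arises only if supply remains and is not carried forward.

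This is a secondary process outcome in a 30-dyad pilot. The change is a cheap improvement, best made before 3-month data are collected.

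**What to change.** 1. At visit 2, record the agreed regimen as planned medication days per week, together with the supply on hand.
2. Credit that supply in the 3-month window, and state the window and the carry-over rule.
3. For decisions that differ only on non-school days, classify implementation from one short electronic question to parent and adolescent at 3 months, not from fills. Keep dispensing records for the decisions they can confirm.
4. Keep calendar-day coverage as the continuity measure in the pre-post test, with the denominator stated and the same algorithm used before and after. Note beside the result that a change of regimen moves it by design.
5. Report post-visit coverage relative to the agreed regimen alongside it, as the implementation measure. A fully implemented continuing regimen then reads 100% whether it is daily or part-week.

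The cost is two fields at an existing visit and one added electronic contact where only a records request is now planned. Some families will not respond, and for the affected dyads the classification rests on self-report. No treatment or visit changes.
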